6.5.4. Concomitant Medications and Non-drug Treatments

Concomitant medications and non-drug treatments received by participants during the study will be summarized for the Safety Analysis Set.

Concomitant medications refer to all medications which started prior to first dose of study treatment and continued during the on-treatment period (see section 3.5.1) as well as those started during the on-treatment period. Concomitant medications will be coded in the WHO Drug coding dictionary and will be tabulated by Anatomical Therapeutic Chemical (ATC) Classification level 2 and preferred term in descending order of frequency. In case of equal frequency regarding drug class (respectively drug name), alphabetical order will be used. A participant will be counted only once within a given drug class and within a given drug name, even if he/she received the same medication at different times. Preferred Terms will be reported under each ATC class that it is included under within WHO Drug (no primary path is available in WHO Drug).

Concomitant non-drug treatments refer to all non-drug treatments administered during the on-treatment period. Non-drug treatments will be coded with the most current version of MedDRA and will be summarized by MedDRA's SOC and PT in descending order of frequency.

Participants will be counted only once per PT even if he/she received the same treatment multiple times.

Any medications or non-drug treatments, aside from anticancer treatments described in section 6.5.5, which were only administered prior to treatment start will be listed but not summarized.

6.5.5. Subsequent Anticancer Therapies/Procedures

Subsequent Anticancer Therapies and Procedures are defined as therapies entered on the short term follow up in the following:

- 'Concomitant Medications' CRF page with 'Category of Medication' = 'Follow-up Cancer Therapy')
- 'Radiation Treatment' CRF page with 'Subcategory' = 'Curative in intent'
- 'Non-drug Treatments' (with 'Category' = 'On-study Cancer Surgery' and 'Outcome of Procedure' = 'Resected' or 'Partially Resected').

The number and percentage of participants within each category (medication therapy, radiation therapy, and surgeries) will be provided.

Medications will be coded using the WHO Drug coding dictionary and will be tabulated by preferred term in descending order of frequency.

Analyses will be based on the safety analysis set.

6.6. Safety Summaries and Analyses

Summaries of safety parameters will be based on the safety analysis set.

6.6.1. Laboratory Data

Laboratory results will be converted to International System of Units (Système International d'unités, SI) units which will be used for applying toxicity grades and for all summaries.

Quantitative data will be summarized using simple descriptive statistics (mean, Std Dev, median, quartiles, minimum, and maximum) of actual values and change from baseline for each nominal visit over time (i.e. unscheduled assessments will be excluded). The total number of participants for change from baseline will include all participants who have both a baseline and a value at the nominal visit.

As described in Section 3.4, baseline will be defined as the last assessment performed on or prior to date of the first dose of study treatment. If there are multiple assessments that meet the baseline definition on the same day without the ability to determine which was truly last, then the worst grade will be assigned as the baseline grade. Several of the CTCAE terms (including Hypo/Hypercalcemia, Chronic Kidney Disease, and Activated Partial Thromboplastin) can be derived using several laboratory tests (analytes).

Results collected as strict inequalities (e.g., >10, <10) will be converted to numeric values subtracting a factor of <0.001>. Expressions of the form" \geq " or " \leq " will be converted to the end point. These numeric values will be evaluated for clinically significant abnormalities but will not be included in calculations of summary statistics.

Additionally, laboratory results will be programmatically classified according to NCI-CTCAE version 4.03 grade. Non-numerical qualifiers will not be taken into consideration in the derivation of grade (e.g. hypokalemia Grade 1 and Grade 2 are only distinguished by a non-numerical qualifier and therefore Grade 2 will not be derived). In summary statistics the number and percentage of participants corresponding to grades that only include non-quantitative criteria will be displayed as a blank or NA (not assessed) rather than 0. If there is any overlap between grade criteria (e.g. CTCAE grading criteria for Creatinine Increased – a value can fall into one range based on comparison to Upper Limit of Normal (ULN) and another range based on comparison to baseline), the highest (worst) grade would be assigned to that record. Grade 5 is defined in the CTCAE criteria guidance as an event with an outcome of death. Since laboratory data does not collect an outcome, Grade 5 is not used when programmatically grading laboratory data.

Grade 0 or Outside Toxicity Reference (OTR) is not defined specifically by in the CTCAE guidance. However, programmatically this is used as a category to represent those participants who did not meet any of the Grades 1 to 4 criteria. If the laboratory value is evaluable for CTCAE criteria grading (numeric value is present, valid units and ranges are present as required to allow conversion to standard units and grading), and does not qualify for any of the Grade 1-4 criteria for a given lab test, then the value is assigned as Grade 0 or OTR.

Several of the CTCAE terms (including Hypo/Hypercalcemia, Chronic Kidney Disease, and Activated Partial Thromboplastin) can be derived using several laboratory tests (analytes).

Abnormalities will be described using the worst grade by scheduled timepoint and overall. Worst case overall will be determined from scheduled and unscheduled visits. Several laboratory tests have bi-directional grading criteria defined so that both low (hypo) and high (hyper) values can be graded separately. Each criterion will be summarized separately. In the cases where a value is graded as a Grade 1, 2, 3, or 4 for one of the directions, that value will also be assigned as a Grade 0 for the opposite direction for that test. For example, a value meeting the criteria for Grade 3 Hypercalcemia will be classified as a Grade 0 Hypocalcemia. For CTCAE terms that can be derived using one of several laboratory tests, the maximum post-baseline grade for a given participant and CTCAE term will be the maximum across all possible laboratory tests.

Additional laboratory results that are not part of NCI-CTCAE will be presented according to the following categories by scheduled timepoint as well as overall: below normal limit, within normal limits, and above normal limits. In the unlikely event that for a given participant, clinically significant abnormalities are noted in both directions (e.g., > ULN and < Lower Limit of Normal (LLN)), then both abnormalities are counted.

Liver function tests: Alanine aminotransferase (ALT), aspartate aminotransferase (AST), Alkaline Phosphatase (ALP), and total bilirubin (TBILI) are used to assess possible drug induced liver toxicity. The ratios of test result over the ULN will be calculated and classified for these three parameters during the on-treatment period.

Summary of liver function tests will include the following categories. The number and percentage of participants with each of the following during the on-treatment period will be summarized:

- ALT $\geq 3 \times ULN$, ALT $\geq 5 \times ULN$, ALT $\geq 10 \times ULN$, ALT $\geq 20 \times ULN$
- AST $\geq 3 \times ULN$, AST $\geq 5 \times ULN$, AST $\geq 10 \times ULN$, AST $\geq 20 \times ULN$
- (ALT or AST) \geq 3×ULN, (ALT or AST) \geq 5×ULN, (ALT or AST) \geq 10×ULN, (ALT or AST) \geq 20×ULN
- TBILI $\geq 2 \times ULN$
- Concurrent ALT $\geq 3 \times ULN$ and TBILI $\geq 2 \times ULN$
- Concurrent AST $\geq 3 \times ULN$ and TBILI $\geq 2 \times ULN$
- Concurrent (ALT or AST) $\geq 3 \times ULN$ and TBILI $\geq 2 \times ULN$
- Concurrent (ALT or AST) \geq 3×ULN and TBILI \geq 2×ULN and ALP > 2×ULN
- Concurrent (ALT or AST) \geq 3×ULN and TBILI \geq 2×ULN and ALP \leq 2×ULN or missing

Concurrent measurements are those occurring on the same date.

Categories will be cumulative, i.e., a participant with an elevation of AST \geq 10×ULN will also appear in the categories \geq 5×ULN and \geq 3×ULN. Liver function elevation and possible Hy's Law cases will be summarized using frequency counts and percentages.

An evaluation of Drug-Induced Serious Hepatotoxicity (eDISH) plot will also be created, with different symbols for different treatment arms, by graphically displaying

- peak serum ALT(/ULN) vs peak total bilirubin (/ULN) including reference lines at ALT=3×ULN and total bilirubin=2×ULN.
- peak serum AST(/ULN) vs peak total bilirubin (/ULN) including reference lines at AST=3×ULN and total bilirubin=2×ULN.

In addition, a listing of all TBILI, ALT, AST and ALP values for participants with a post-baseline TBILI $\geq 2 \times \text{ULN}$, ALT $\geq 3 \times \text{ULN}$ or AST $\geq 3 \times \text{ULN}$ will be provided.

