5.1. Hypotheses and Decision Rules

5.1.1. Hypotheses and Sample Size

The primary objective of the study is to evaluate the safety and tolerability of single-agent lorlatinib in participants with unresectable advanced and/or recurrent ALK-positive NSCLC with resistance or intolerance to at least 1 prior ALK inhibitor treatment. No formal statistical hypothesis testing is planned for the primary objective.

This study will enroll enough participants to ensure that 100 participants are treated with lorlatinib.

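### The SAP carries laboratory results reported as `>x` as x − 0.001, which can place a result one category too low when the reporting limit sits on a cut-off

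*SAP*

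**What the plan says.** The rule is in SAP 6.6.1 (Laboratory Data). It covers both directions: "Results collected as strict inequalities (e.g., >10, <10". For all of these the operation is the same: they "will be converted to numeric values subtracting a factor of <0.001>". Results reported with ≥ or ≤ are treated differently and "will be converted to the end point". Neither the SAP nor the protocol has a separate rule for `>`.

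The same paragraph states how the converted numbers are used: "These numeric values will be evaluated for clinically significant abnormalities but will not be included in calculations of summary statistics".

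Later in the same section, "laboratory results will be programmatically classified according to NCI-CTCAE version 4.03 grade". The condition for a value to be gradable begins: "If the laboratory value is evaluable for CTCAE criteria grading (numeric value is present, valid units and ranges are present". The section goes on to count ALT and AST at or above 3, 5, 10 and 20 × ULN, total bilirubin at or above 2 × ULN, and the concurrent combinations. Tests without a CTCAE grade are classed as below, within or above normal limits.

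**The concern.** Subtracting a small amount is right for `<x`, because the true value lies below x. It is wrong for `>x`, because the true value lies above x. Under the written rule, two results on opposite sides of the same limit receive the same number. A result known to exceed the limit also ranks below one reported as `≥x`, which may only equal it.

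The converted numbers are used to decide whether a result counts as abnormal. If a laboratory's upper reporting limit happens to equal a cut-off, a `>x` result fails a category that it is known to meet. In the high direction that error can only lower the count. Elsewhere SAP 6.6.1 leans the other way: where grading criteria overlap, or same-day baseline results cannot be ordered, it takes the worst grade.

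Tests are run at local laboratories (Protocol 7.2.4 and Appendix 6) in a multicenter study, so reporting limits may differ between sites.

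**Working it through.** **Inputs from SAP 6.6.1:** strict inequalities in both directions; subtract 0.001; ≥ and ≤ go to the end point; liver cut-offs at 3, 5, 10 and 20 × ULN. There is no sample size, power or error rate to reproduce: the point concerns a data-conversion rule, and the SAP states that "No formal statistical hypothesis testing is planned for the primary objective".

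**Assumption:** ULN = 40 U/L for ALT, for illustration only. The documents give no ULN and no reporting limits.

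**Step 1. The SAP's own example.**

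| Reported | Written rule | Direction-specific rule |
|---|---|---|
| `<10` | 10 − 0.001 = 9.999 | 9.999 |
| `≤10`, `≥10` | 10 | 10 |
| `>10` | 10 − 0.001 = 9.999 | 10 + 0.001 = 10.001 |

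The written rule ties `>10` with `<10` and puts both below `≥10`. The direction-specific rule restores the order.

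**Step 2. Reporting limit exactly on a liver cut-off (x = k × 40).**

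| k | Reported | Written rule | Meets ≥ k × ULN? | With x + 0.001 | Meets it? |
|---|---|---|---|---|---|
| 3 | `>120` | 119.999 | No | 120.001 | Yes |
| 5 | `>200` | 199.999 | No | 200.001 | Yes |
| 10 | `>400` | 399.999 | No | 400.001 | Yes |
| 20 | `>800` | 799.999 | No | 800.001 | Yes |

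For k = 3 the written rule gives 119.999 / 40 = 2.999975 × ULN. The failure does not depend on the assumed ULN: for any ULN, if x = k × ULN then x − 0.001 is below k × ULN.

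**Step 3. Above or within normal.** With an upper limit of 40, `>40` becomes 39.999, which is not above 40. With x + 0.001 it becomes 40.001, which is.

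**Step 4. Reporting limit away from a cut-off.** `>1000` becomes 999.999 / 40 = 24.999975 × ULN under the written rule and 1000.001 / 40 = 25.000025 × ULN under the other. Both are above 20 × ULN, so the category is the same.

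**Step 5. When does it bite?** For a cut-off of the form ≥ c, a `>x` result is known to meet it if x ≥ c. The written rule fails it if x − 0.001 < c. Both hold when c ≤ x < c + 0.001. For c = 120, limits of 120 and 120.0005 fail; 120.001 and 121 pass.

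**Step 6. Units.** The SAP converts results to SI units but does not say whether 0.001 is taken off before or after. With a conversion factor f, the result is f(x − 0.001) or fx − 0.001. Both lie below fx, so the direction of the error is the same. Only the width of the window in Step 5 changes.

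**Step 7. Link to CTCAE grade.** The conversion sentence speaks of abnormalities, not grades. The link comes from the later text, which treats a result with a numeric value, valid units and ranges as gradable. A converted result has a numeric value, so on a plain reading it is graded. This is a sound inference rather than an explicit statement.

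**The case against.** The strongest reply accepts that the sentence is a drafting error and disputes its consequence. The angle brackets around 0.001 look like a template field left unedited, and a programmer may well code `>` correctly anyway. That does not rescue the text. Coding it correctly would depart from the SAP as written, and SAP section 2 says deviations from the plan will be described in the Clinical Study Report.

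The rest of the reply concerns scope, and most of it stands.

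- **No coincidence is shown.** The documents give no reporting limits, ULNs or number of laboratories. The ALT example was chosen so that the limit equals 3 × ULN. A reader might infer that `>x` results are misgraded in general, or that high-direction toxicity will be under-counted in this study. The documents support neither: Step 4 shows no effect away from a cut-off.
- **The primary endpoint is not touched.** A reader might infer that it is, because safety is the primary objective. But the endpoint is adverse event incidence, and toxicity grade, seriousness and relatedness are as the investigator reports them (SAP 6.1.1.1). Abnormal tests become adverse events under Protocol 8.5, without this conversion.
- **Descriptive statistics are not touched**, because converted values are excluded from them.
- **Site reporting of potential Hy's law cases is not touched.** Sites work from the actual results and report such cases as serious adverse events (Protocol 8.6.2 and Appendix 6, Table 6, footnote 1). A reader might infer that cases would be missed altogether; what could be lost is a count in a SAP table.

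The SAP's liver listing is only a partial backstop. A participant with ALT `>120` and bilirubin at or above 2 × ULN is listed through bilirubin, and a qualifying AST would still fill the combined ALT-or-AST rows. If ALT is the only qualifying value and the listing is programmed on converted values, the participant drops out of the listing too.

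**Conclusion.** Wrong as written, with minor impact. The literal rule stores `>x` as x − 0.001, equal to `<x` and below `≥x`, and nothing else in the SAP or protocol corrects it.

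The effect on any one result is either nothing or one category. It is one category only when the reporting limit is at the cut-off or less than 0.001 above it, in the units used. It is confined to the programmatic laboratory tables and to any listing or display built on the converted values. How often it would occur cannot be determined from the documents and may well be rarely or never.

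The conclusion assumes that the sentence is programmed literally. For CTCAE grade, it also assumes that converted values enter the grading, as Step 7 infers. It does not depend on the illustrative ULN of 40.

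**What to change.** Replace the strict-inequality sentence in SAP 6.6.1 with:

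*Results recorded as* `<x` *are converted to x minus 0.001 and results recorded as* `>x` *to x plus 0.001, applied in the reported units before SI conversion; these values remain excluded from summary statistics.*

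The existing end-point rule for ≥ and ≤ can stay. The new wording also removes the stray angle brackets and settles the order relative to SI conversion.

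The cost is one sentence in the SAP and about one line of code. No new data are needed, and the design, sample size and primary analysis do not change.

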## 5.3. Administration

The product will be administered in accordance with the label.

The recommended dosage of lorlatinib is 100 mg orally QD, with or without food, until disease progression, unacceptable toxicity, or participant refusal/lost to follow-up. Tablets should be swallowed whole. Tablets should not be chewed, crushed, or split. Tablets should not be taken if they are broken, cracked, or otherwise not intact. Lorlatinib should be taken at the same time each day. If a dose is missed, then the missed dose should be taken unless the next dose is due within 4 hours. Two (2) doses should not be taken at the same time to make up for a missed dose. An additional dose should not be taken if vomiting occurs after lorlatinib but the next scheduled dose should be continued. Dosing interruption or dose reduction may be required based on individual safety and tolerability.

Lorlatinib dose reduction levels are summarized below:

- First dose reduction: 75 mg taken orally QD;
- Second dose reduction: 50 mg taken orally QD.

Lorlatinib should be permanently discontinued if the participant is unable to tolerate the 50 mg dose taken orally QD. Dose modification recommendations for adverse reactions are provided in Table 2.

Adverse Reaction	Lorlatinib Dosing
CNS Effect	
Grade 1	Continue lorlatinib at same dose or withhold the
	dose until recovery to baseline. Resume lorlatinib at
	the same dose or at a reduced dose.
Grade 2 or Grade 3	Withhold dose until Grade 0 or 1. Resume lorlatinib
	at a reduced dose.
Grade 4	Permanently discontinue lorlatinib.
Hyperlipidemia	
Grade 4 hypercholesterolemia or Grade 4	Withhold lorlatinib until recovery of
hypertriglyceridemia	hypercholesterolemia and/or hypertriglyceridemia to
	less than or equal to Grade 2. Resume lorlatinib at
	the same dose. If severe hypercholesterolemia
	and/or hypertriglyceridemia recurs, resume lorlatinit
	at a reduced dose.
AV block	
Second-degree AV block	Withhold lorlatinib until PR interval is less than
	200 msec. Resume lorlatinib at a reduced dose.
First occurrence of complete AV block	Withhold lorlatinib until:
	
 
pacemaker placed, or
 

	• PR interval less than 200 msec.
	If a pacemaker is placed, resume lorlatinib at the
	same dose. If no pacemaker is placed, resume
	lorlatinib at a reduced dose.
Recurrent complete AV block	Place pacemaker or permanently discontinue
	lorlatinib.
ILD/Pneumonitis	
Any grade treatment-related ILD/Pneumonitis	Permanently discontinue lorlatinib.

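### Laboratory results reported only as inequalities are left out of the by-visit descriptive statistics, which biases those tables by an amount that depends on how many such results there are

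*SAP*

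**What the plan says.** SAP 6.6.1 (Laboratory Data) sets three rules that meet here.

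- **What is summarised.** "Quantitative data will be summarized using simple descriptive statistics (mean, Std Dev, median, quartiles, minimum, and maximum) of actual values and change from baseline", by nominal visit. For change, "The total number of participants for change from baseline will include all participants who have" both a baseline value and a value at that visit.
- **How inequality results become numbers.** "Results collected as strict inequalities (e.g., >10, <10) will be converted to numeric values subtracting a factor of <0.001>". Non-strict inequalities "will be converted to the end point".
- **What those numbers are used for.** "These numeric values will be evaluated for clinically significant abnormalities but will not be included in calculations of summary statistics".

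The same section also plans grading: "Additionally, laboratory results will be programmatically classified according to NCI-CTCAE version 4.03 grade". SAP 3.5.3 adds a shift table of baseline grade against maximum post-baseline grade.

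**The concern.** A result reported as `>x` is removed because it is high, and one reported as `<x` because it is low. This is not ordinary missing data. The results that remain are a truncated sample, and the median, quartiles and mean computed from them describe only the part of the distribution inside the reporting limits. This is so whatever number the conversion rule assigns.

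Change from baseline is affected through the pair. A participant with a numeric baseline and `>x` on treatment has a value at that visit, yet contributes nothing to the change statistics there. If the baseline itself is an inequality, the participant drops out of change at every visit.

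The point is relevant to this trial because safety is the primary objective, lipids are measured at every cycle, and Table 2 in Protocol 5.3 provides for "Grade 4 hypercholesterolemia or Grade 4" hypertriglyceridemia. Grade tables count how many participants crossed a threshold. The by-visit tables are where a reader looks for the size of the shift, and that is the quantity this rule distorts.

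**Working it through.** The plan states no figure for this rule, so there is nothing to reproduce. The check has four parts.

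**1. Does anything else in the plan restore these results?** No. SAP 5.3 evaluates data as observed, without imputation unless otherwise specified. SAP 5.2.12 reports the number of non-missing and missing values for continuous variables, but not how many were excluded for lying beyond a limit. No sensitivity summary is planned.

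**2. Effect on the median and quartiles, with no distribution assumed.** Suppose a share p of the results at a visit lies above one common upper limit and is dropped. The reported median is then the true (1-p)/2 quantile, and the reported upper quartile is the true 0.75(1-p) quantile.

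- p=5%: the 47.5th and 71.25th percentiles are reported as the median and Q3.
- p=10%: the 45th and 67.5th.
- p=20%: the 40th and 60th.

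**3. Effect in per cent.** Assumptions: actual values lognormal with log-SD s=0.6, one common upper limit, no lower limit. None of these inputs, nor p, is in the documents. With z the standard normal quantile and Φ its distribution function:

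- median ratio = exp(s·z((1-p)/2))
- Q3 ratio = exp(s·[z(0.75(1-p)) - z(0.75)])
- mean ratio = Φ(z(1-p) - s)/(1-p)

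Example at p=10%:

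- Median: z(0.45) = -0.1257, and exp(0.6 × -0.1257) = 0.927, a shift of -7%.
- Q3: z(0.675) - z(0.75) = 0.4538 - 0.6745 = -0.2207, and exp(0.6 × -0.2207) = 0.876, a shift of -12%.
- Mean: Φ(1.2816 - 0.6)/0.9 = 0.7522/0.9 = 0.836, a shift of -16%.

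| p | Median | Q3 | Mean |
|---|---|---|---|
| 1% | -0.7% | -1.4% | -3.3% |
| 5% | -4% | -7% | -10% |
| 10% | -7% | -12% | -16% |
| 20% | -14% | -22% | -26% |

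The spread matters too. At p=10% the median shift is -4.9% for log-SD 0.4 and -9.6% for log-SD 0.8. A lower limit produces shifts in the opposite direction.

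**4. Change from baseline.** This needs further assumptions: a baseline-to-visit correlation of 0.6 on the log scale and a true 1.5-fold rise. Simulation of 2,000,000 pairs per scenario, with one common limit and pairs dropped if either value exceeds it, gave these biases in the mean change:

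| p | Excluded, log-SD 0.4 | Kept at limit, log-SD 0.4 | Excluded, log-SD 0.8 | Kept at limit, log-SD 0.8 |
|---|---|---|---|---|
| 1% | -3.4% | -1.1% | -9.8% | -4.0% |
| 5% | -11.1% | -5.0% | -25.9% | -14.2% |
| 10% | -17.9% | -9.7% | -37.2% | -23.8% |
| 20% | -28.1% | -19.1% | -51.4% | -39.2% |

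In the same simulation, keeping values at the limit left the median of actual values unbiased. It reduced the bias in the mean change without removing it, because a change computed at the limit is only a lower bound when the on-treatment value is the censored one.

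**The case against.** The strongest reply is that little depends on these tables. The laboratory analysis in Protocol 9.6 consists of CTCAE grading, abnormalities by maximum grade, normal-range categories and shift tables; the by-visit laboratory statistics appear only in the SAP. Inequality results are expressly kept for abnormality evaluation, so this exclusion does not hide a Grade 3 or 4 lipid rise from the grade tables. The primary endpoint is adverse event incidence, and there is no hypothesis test, decision rule or comparator. All of this stands, and it confines the point to descriptive tables.

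The second reply is that p may be close to zero. Table 2 shows that severe lipid rises are foreseen; it does not show that any laboratory would report them as `>x` rather than as a number. Dosing is withheld at Grade 4, and lipid-lowering therapy is provided for. With about 100 participants, p=1% is one person, and the median then moves by 1% or less. Under log-SD 0.6 and n=100, the sampling standard error of the log median is about 0.6 × √(π/2)/√100 = 0.075, which exceeds the -4% bias at p=5%. This also stands as a limit on size. It does not justify the rule, since the bias has a known direction.

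Three stronger readings are tempting, and the documents do not support them.

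- A reader might infer that exactly the most extreme results in the trial are lost and that the reported maximum is capped at the assay limit. That needs one common limit. Protocol 7.2.4 uses local laboratories, so a higher numeric result from another site can remain. In an illustration where half the samples were subject to a limit and 5% of all results were dropped, about 50% of the top 5% were retained.
- A reader might infer that the tables always move toward normal. That fits upper-limit results only. Dropping `<x` results moves the statistics upward, and such values may be clinically normal.
- A reader might infer that the planned tables will understate the lipid effect of lorlatinib. That needs on-treatment results to be reported as `>x` more often than baseline results, and the documents say nothing on this.

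**Conclusion.** The point holds as a limited one. SAP 6.6.1 drops laboratory results from the by-visit descriptive statistics because of their value, and no other section restores or counts them. Removing `>x` results lowers the median, quartiles and mean of actual values, and lowers change from baseline when the on-treatment value is the one removed. Removing `<x` results does the reverse.

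The direction follows from the rule; the size cannot be determined from the documents. It is negligible if few results are reported as inequalities. Under lognormal values with log-SD 0.6 and one common limit, the median of actual values shifts by about -4% at p=5% and -7% at p=10%. CTCAE grade tables, shift tables and adverse event incidence are not affected by this exclusion. The change is worth making because it is cheap and replaces a stated rule, not because any main conclusion of the trial is at risk.

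**What to change.** Replace the exclusion sentence in SAP 6.6.1, and for summary statistics also replace the conversion that subtracts 0.001, with the following:

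1. **Actual values.** Keep inequality results at the reporting limit itself in the median, quartiles, minimum and maximum. Where a statistic falls on such a result, print it as `>x` or `<x`.
2. **Counts.** Report the number of inequality results per analyte and visit.
3. **Change from baseline.** Include these participants, using the limit for the censored value.
4. **Footnotes.** At affected visits, mark the mean of actual values and all change-from-baseline statistics (mean, median and quartiles) as bounds. The median and quartiles of change need the mark as well, because a change computed at the limit need not rank at the top. State the direction: `>x` at the visit makes the change a lower bound, while `>x` at baseline makes it an upper bound.

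The cost is a short SAP revision and minor programming. The downside is that the footnoted statistics become bounds rather than exact values. No endpoint or clinical rule changes.
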